5.2 Evaluability

All patients who receive any study treatment are evaluable for toxicity. Patients are evaluated from first receiving study treatment until a 30-day follow up after the conclusion of treatment or death.

All patients are evaluable for disease response unless they discontinue treatment due to treatment related adverse events(s) prior to completion of a first disease assessment.

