1.2 Palbociclib (Ibrance)

Palbociclib (Ibrance, Pfizer) is a highly selective small-molecule inhibitor of CDK4 and CDK6, which can be administered orally. It results in loss of RB1 phosphorylation in vitro and leads to cell cycle arrest at the G1-S phase in ER+ breast cancer (8). While initial phase 2 studies demonstrated single agent activity in hormone receptor positive breast cancer (9), subsequent studies have reported synergistic activity with endocrine therapies in ER+/PR+ breast cancer. In preclinical studies, palbociclib was effective in both tamoxifen sensitive and resistant ER+ breast cancer cell lines (7).

An open-label randomized phase 2 study involving postmenopausal patients with newly diagnosed metastatic ER+ and human epidermal growth factor receptor (Her-2/neu) negative breast cancer (PALOMA1), showed that palbociclib in combination with letrozole was associated with significantly prolonged PFS when compared with letrozole alone (10). This resulted in an accelerated FDA approval of palbociclib for use in this specific patient population (11). In this trial, 27 patients in the palbociclib plus letrozole group (33%) had dose interruptions because of adverse events, compared with only three (4%) patients in the letrozole group. In the combination group, 37 (45%) patients required a delay in the start of a subsequent treatment cycle because of an adverse event and 33 (40%) patients had a dose reduction. In this study, 11 (13%) patients in the palbociclib plus letrozole group

and two (2%) patients in the letrozole group discontinued the study because of an adverse event. Of these discontinuations, six (7%) patients in palbociclib plus letrozole group and two (2%) patients in the letrozole group discontinued because of treatment-related adverse events.

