2.2 Secondary Objectives

1. To determine the rate of grade 3 or higher neutropenia in patients with hormone receptor positive breast cancer treated with palbociclib on a 5 days on/2 days off schedule during all cycles.
2. To determine the rate of palbociclib dose reduction, interruption, or discontinuation.
3. To determine the adverse events profile of palbociclib given on a 5 days on/2 days off schedule.
4. To determine the progression free survival in patients with hormone receptor positive breast cancer treated with palbociclib on a 5 days on/2 days off schedule.
5. To determine the overall response rate (CR+PR) in patients with hormone receptor positive breast cancer treated with palbociclib on a 5 days on/2 days off schedule.
6. To determine the clinical benefit rate (CR+PR+SD for at least 6 months) in patients with hormone receptor positive breast cancer treated with palbociclib on a 5 days on/2 days off schedule.

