3.0 PATIENT SELECTION

3.1 Inclusion Criteria

1. Histologically confirmed metastatic ER+ and/or PR+ and HER2- breast cancer who are candidates for palbociclib in combination with either letrozole or fulvestrant per treating physician.
2. Presence of measurable or non-measurable disease by RECIST 1.1 criteria.
3. One prior systemic therapy in the metastatic setting is allowed, but patients who have not had any prior systemic therapies in the metastatic setting are also eligible.
 - Note: patients who were started on endocrine therapy monotherapy as their 1st line or 2nd line systemic therapy in the metastatic setting for no more than 28 days and without clinical progression prior to the initiation of the study drug therapy are allowed to enroll on the study as their 1st line or 2nd line therapy, respectively.
4. At least 18 years of age.
5. ECOG performance status ≤ 2 (see Appendix A)

6. Normal bone marrow and organ function as defined below:
 - a. Absolute neutrophil count $\geq 1,500/\text{mcl}$
 - b. Platelets $\geq 100,000/\text{mcl}$
 - c. Total bilirubin $\leq \text{IULN}$ or total bilirubin $\leq 3.0 \times \text{IULN}$ with direct bilirubin within normal range in patients with documented Gilbert's syndrome
 - d. AST(SGOT)/ALT(SGPT) $\leq 1.5 \times \text{IULN}$ (up to $5 \times \text{IULN}$ in patients with liver disease)
 - e. Creatinine $\leq \text{IULN}$ OR creatinine clearance $\geq 60 \text{ mL/min/1.73 m}^2$ for patients with serum creatinine levels above institutional normal (IULN) (calculated by Creatinine Clearance Estimate by Cockcroft-Gault Equation)
7. Pre- or post-menopausal women are allowed. If pre- or peri-menopausal, concurrent ovarian suppression for pre- or peri-menopausal women is required.
8. Women of childbearing potential must agree to use adequate contraception (hormonal or barrier method of birth control, abstinence) prior to study entry and for the duration of study participation. Should a woman become pregnant or suspect she is pregnant while participating in this study, she must inform her treating physician immediately.
9. Able to swallow and retain oral medication.
10. Washout of at least 3 weeks from prior chemotherapy or targeted therapy that induces myelosuppression and recovery of treatment related adverse events to grade 1 or less, with the exception of alopecia, is required prior to the start of palbociclib.

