11.0 DATA SUBMISSION SCHEDULE

Case report forms with appropriate source documentation will be completed according to the schedule listed in this section.

Case Report Form	Submission Schedule
Original Consent Form	Prior to registration
On-Study Form	Prior to starting treatment
Treatment Form	Every cycle ¹ and end of treatment
Toxicity Form	Continuous
Treatment Summary Form	Completion of treatment
Specimen Collection Form	Per protocol
Follow Up Form	30 Day follow-up
Tumor Measurement Form	Baseline, end of every 2 nd or 3 rd cycle, and end of treatment

¹At physician discretion, patients that have been on a stable dose of Palbo for 6 consecutive cycles, may dose in q2-3 cycle intervals to coincide with tumor imaging studies. The treatment data forms will be completed accordingly.

Any queries generated by Washington University must be responded to within 28 days of receipt by the participating site. The Washington University research team will conduct a regular review of data status at all secondary sites, with appropriate corrective action to be requested as needed.

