12.4.3 Evaluation of Best Overall Response

The best overall response is the best response recorded from the start of the treatment until disease progression/recurrence (taking as reference for progressive disease the smallest measurements recorded since the treatment started). The patient's best response assignment will depend on the achievement of both measurement and confirmation criteria.

For Patients with Measurable Disease (i.e., Target Disease)

Target Lesions	Non-Target Lesions	New Lesions	Overall Response	Best Overall Response when Confirmation is Required*
CR	CR	No	CR	>4 wks. Confirmation**
CR	Non-CR/Non-PD	No	PR	>4 wks. Confirmation**
CR	Not evaluated	No	PR	
PR	Non-CR/Non-PD/not evaluated	No	PR	
SD	Non-CR/Non-PD/not evaluated	No	SD	Documented at least once >4 wks. from baseline**
PD	Any	Yes or No	PD	no prior SD, PR or CR
Any	PD***	Yes or No	PD	
Any	Any	Yes	PD	

* See RECIST 1.1 manuscript for further details on what is evidence of a new lesion. ** Only for non-randomized trials with response as primary endpoint. *** In exceptional circumstances, unequivocal progression in non-target lesions may be accepted as disease progression. Note: Patients with a global deterioration of health status requiring discontinuation of treatment without objective evidence of disease progression at that time should be reported as “symptomatic deterioration.” Every effort should be made to document the objective progression even after discontinuation of treatment.
				

For Patients with Non-Measurable Disease (i.e., Non-Target Disease)

Non-Target Lesions	New Lesions	Overall Response
CR	No	CR
Non-CR/non-PD	No	Non-CR/non-PD*
Not all evaluated	No	not evaluated
Unequivocal PD	Yes or No	PD
Any	Yes	PD

* ‘Non-CR/non-PD’ is preferred over ‘stable disease’ for non-target disease since SD is increasingly used as an endpoint for assessment of efficacy in some trials so to assign this category when no lesions can be measured is not advised
		

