15.2 Sample Size Calculations

The rate of grade 3 or higher neutropenia in PALOMA -1 and PALOMA – 3 was 54% and 62% respectively. We anticipate the new schedule to have less toxicity leading to around 40%-50% AE rate. The sample size was calculated to test the one-sided null hypothesis that 1-AE (adverse event) rate ≤ 0.38 (i.e., AE rate >0.62) versus the alternative that 1-AE rate ≥ 0.6 (i.e., AE rate <0.4). Enrollment of 47 patients will be required to achieve 90% power (actual power=91.8%) based on one-sample binomial exact test at a 5% level (actual alpha=4.7%). If no grade 3 or higher adverse events were observed on 24 or more patients on the alternative dosing schedule, the alternative dosing will be deemed to show better toxicity profile than standard schedule.

The CBR was estimated as 84.3% (80%~88%) in 1st line and 67% from PALOMA-3 in 2nd line patients. With an estimation that 70% of the enrolled patients are 2nd line, we expect approximately 33 2nd line patients and 14 1st line patients and thus ~22 2nd line patients with ~11 1st line patients with clinical benefit. With 33 2nd line patients, the CBR can be estimated with a 95% two-sided Clopper-Pearson exact CI of 48.5~82.3% given the true CBR is 67% as in PALOMA-3 while the CBR in the 14 1st line patients can be estimated with a 95% CI of 55.5%~97.7% given the true CBR is 84.3%.

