15.3 Data Analysis Plan

Patient characteristics and adverse events profiles will be summarized by descriptive statistics. AE rate, ORR, CBR will each be estimated accompanied with 95% confidence interval (CI). PFS will be analyzed by Kaplan-Meier method and 1-year PFS rate will be estimated with 95% CI. All analyses will be conducted among all patients, as well as by subgroups of interest (e.g., line of therapy).

TK1 serum marker will be correlated with absolute neutrophil count along measured time points and tumor response by Pearson or Spearman correlation coefficient as appropriate.

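### The plan does not say whether ORR and CBR use all treated patients or the Section 5.2 set, which drops early stops for treatment-related toxicity

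*Combined protocol and SAP*

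**What the plan says.** Section 5.2 (Evaluability) has two rules. For toxicity, anyone who received study treatment counts. For response, all patients are "evaluable for disease response unless they discontinue treatment due to treatment related adverse events(s) prior to completion of a first disease assessment".

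Section 15.3 (Data Analysis Plan) says that ORR and CBR will each be estimated with a 95% confidence interval, and then: "All analyses will be conducted among all patients, as well as by subgroups of interest", with line of therapy as the example. It names no response-evaluable set and does not refer to 5.2.

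Section 15.2 (Sample Size Calculations) plans CBR precision by line of therapy: "we expect approximately 33 2nd line patients and 14 1st line patients". These add to the full enrolment of 47, with no allowance for unevaluable patients. About 22 and 11 of them are expected to have clinical benefit. Section 15.2 gives no planning value for ORR.

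The secondary objectives (2.2) and the response criteria (12.4) define ORR and CBR by response category and state no denominator. Nor do they say how a patient with no post-baseline assessment counts in either rate.

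**The concern.** Two analysts working from this document could report different ORR and CBR values from the same data, and each could point to text in support.

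The two versions are not equally neutral. The 5.2 rule removes patients because of treatment-related toxicity, and tolerability of the new schedule is the trial's main question. A patient who could not tolerate the drug long enough to be scanned has usually not benefited, so removing her usually raises the rate. The rule is also selective: a patient who stops equally early by withdrawal, or for an event judged unrelated, stays in. In a single-arm trial, a judgment about causality would then set the denominator.

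At stake are two secondary estimates, reported overall and by line of therapy. Section 15.2 sets CBR expectations from earlier trials, so a reader is likely to compare the results with those rates.

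**Working it through.** **Reproducing the plan's figures.** Clopper-Pearson 95% limits, using the unrounded expected counts:
- Second line: 0.67 × 33 = 22.11 of 33 gives 48.5% to 82.3%, as stated in 15.2.
- First line: 0.843 × 14 = 11.80 of 14 gives 55.5% to 97.7%, as stated.

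The planned intervals therefore use the full denominators. Their half-widths are (82.3 − 48.5)/2 = 16.9 points and (97.7 − 55.5)/2 = 21.1 points.

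For the primary test, 24 or more of 47 gives an exact alpha of 4.7% at 0.38 and power of 91.8% at 0.60, both as stated. Toxicity evaluability needs only some study treatment, so the response rule does not touch this test.

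**Shift in CBR for k exclusions.** Take 22 + 11 = 33 benefits and suppose none of the k excluded patients has documented benefit. The two rates are 33/47 and 33/(47 − k).

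| k | CBR | 95% CI | Shift (points) |
|---|---|---|---|
| 0 | 33/47 = 70.2% | 55.1–82.7 | – |
| 1 | 33/46 = 71.7% | 56.5–84.0 | +1.5 |
| 2 | 33/45 = 73.3% | 58.1–85.4 | +3.1 |
| 3 | 33/44 = 75.0% | 59.7–86.8 | +4.8 |

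By line, with one exclusion:
- First line: 11/14 = 78.6% becomes 11/13 = 84.6%, +6.0 points.
- Second line: 22/33 = 66.7% becomes 22/32 = 68.8%, +2.1 points.

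ORR has no planning value, but any rate over all 47 is multiplied by 47/(47 − k): 47/46 = 1.022 for k = 1 and 47/44 = 1.068 for k = 3.

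**How large k might be.** The documents do not give k. Section 1.2 supplies discontinuation rates over whole treatment periods:
- First line, phase 2 study: 7% for treatment-related events ("Of these discontinuations, six (7%) patients in palbociclib plus letrozole group").
- First line, phase 3 study: 9.7% for any adverse event.
- Second line, phase 3 fulvestrant study: 2.6% for any adverse event.

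Expected k = 14 × (first-line rate) + 33 × (second-line rate):
- 7% and 2.6%: 0.98 + 0.86 = 1.8. With independent binomials, P(k ≥ 3) = 28%.
- 9.7% and 2.6%: 1.36 + 0.86 = 2.2, with P(k ≥ 3) = 38%.

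Only stops before the first assessment count. Section 12.1 puts that at 12 weeks, and the study calendar at the end of cycle 2 or 3 (8 to 12 weeks). If 25% or 50% of the stops at 7% and 2.6% come that early (an assumption), expected k is 0.46 or 0.92, and P(k ≥ 3) is 1% or 6%.

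**Direction.** The shift is upward unless an excluded patient has benefit documented later. One such patient gives 32/46 = 69.6%, which is 0.6 points below 70.2%. This is possible on paper because Section 11.0 requires the tumor measurement form at "Baseline, end of every 2 nd or 3 rd cycle, and end of treatment".

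**The case against.** The strongest reply is that there is no contradiction. In 15.3, the phrase about all patients is set against subgroups, so it may mean only the whole cohort. Section 5.2 is the specific rule on response, and specific text ordinarily governs general text. The 33 and 14 in 15.2 are approximate planning inputs from an assumed 70/30 split, not the definition of an analysis set. A prespecified evaluable set is also a legitimate design choice.

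Much of this stands. A reader might infer that 15.3 flatly overrules 5.2, but the documents do not support that. What remains is that no section links the two rules, and the only denominators actually used, in 15.2, are the full ones.

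The reply also says that the effect is slight: the historical rates cover whole treatment periods, two of the three are for any adverse event, and zero or one exclusion is the likely result. That stands, and it sets the size of this point.

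What the reply does not answer is the nature of the rule. Even when prespecified, a denominator that depends on treatment-related toxicity does not estimate the response rate among patients started on the schedule.

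**Conclusion.** The point holds as a minor one. The denominator for ORR and CBR is unresolved, and applying 5.2 would usually make both rates more favourable by conditioning on an outcome of treatment.

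For overall CBR the shift is about 1.5 points with one exclusion and 4.8 with three. A single first-line exclusion moves that subgroup by 6.0 points because it has only 14 patients. The single-exclusion shifts by line (6.0 and 2.1 points) lie well inside the planned half-widths of 21.1 and 16.9 points. These sizes rest on the plan's expected 33 benefits and on an assumed k. The expected values of k are averages, not upper limits.

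Two stronger readings are not supported. A reader might infer that the trial's conclusion is at risk, but the primary endpoint, sample size, alpha, power and decision rule do not depend on response evaluability, and no test or decision uses ORR or CBR. A reader might also infer that the bias is always upward, but a later documented benefit in an excluded patient reverses it.

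How non-measurable disease enters these rates is a separate matter and adds no weight here.

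**What to change.** In 5.2 and 15.3:
- Make all treated patients the primary denominator for CBR and ORR. If ORR is restricted to measurable disease, use all treated patients with measurable disease at baseline.
- Count patients with no post-baseline disease assessment as non-responders without clinical benefit.
- Keep the 5.2 evaluable set only as a sensitivity analysis, and report the number of patients it removes by line of therapy.

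The cost is wording in two sections, with no added procedures or data. The downside is slightly less favourable ORR and CBR. A single sentence linking 15.3 to 5.2 would also remove the ambiguity, but it would leave the toxicity-dependent denominator in place.

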5.3 General Concomitant Medication and Supportive Care Guidelines

While taking palbociclib, patients should be instructed to avoid food or drugs that are known strong CYP3A4 inhibitors or inducers, including grapefruit and grapefruit juice. Please refer to Appendix D for a list of prohibited medications.

No specific antidotes exist for the treatment of palbociclib overdose. Since renal excretion of palbociclib is minimal, the benefit of hemodialysis in the treatment of a palbociclib overdose is probably negligible. The treatment of overdose of palbociclib should consist of general supportive measures. If indicated, elimination of unabsorbed drug should be achieved by emesis or gastric lavage.

5.4 Women of Childbearing Potential

Women of childbearing potential (defined as women with regular menses, women with amenorrhea, women with irregular cycles, women using a contraceptive method that precludes withdrawal bleeding, and women who have had a tubal ligation) are required to have a negative pregnancy test within 7 days prior to the first dose of palbociclib.

Women of childbearing potential are required to use two forms of acceptable contraception, including one barrier method, during participation in the study and for 90 days following the last dose of palbociclib.

If a patient is suspected to be pregnant, all study drugs should be immediately discontinued. In addition, a positive urine test must be confirmed by a serum pregnancy test. If it is confirmed that the patient is not pregnant, the patient may resume dosing.

If a female patient or female partner of a male patient becomes pregnant during therapy or within 90 days after the last dose of palbociclib, the investigator must be notified in order to facilitate outcome follow-up.

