3.2 Exclusion Criteria

1. Prior therapy with any CDK inhibitor.
2. Currently receiving any other investigational agents.
3. Currently receiving exogenous estrogen replacement therapy (topical vaginal estrogen therapy is allowed).
4. Known brain metastases. Patients with known brain metastases must be excluded from this clinical trial because of their poor prognosis which could affect the evaluation of all-cycle adverse events.
5. A history of allergic reactions attributed to compounds of similar chemical or biologic composition to palbociclib or other agents used in the study.
6. Receiving any medications or substances that are potent inhibitors or inducers of CYP3A isoenzymes within 7 days prior to registration.

7. Clinically significant history of liver disease.
8. A condition that would interfere with enteric absorption.
9. Uncontrolled intercurrent illness including, but not limited to, ongoing or active infection, symptomatic congestive heart failure, unstable angina pectoris, or cardiac arrhythmia.
10. Pregnant and/or breastfeeding. Women of childbearing potential must have a negative pregnancy test within 7 days of study entry.
11. Known HIV-positivity on combination antiretroviral therapy because of the potential for pharmacokinetic interactions with palbociclib. In addition, these patients are at increased risk of lethal infections when treated with marrow-suppressive therapy. Appropriate studies will be undertaken in patients receiving combination antiretroviral therapy when indicated.

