4.0 REGISTRATION PROCEDURES

Patients must not start any protocol intervention prior to registration through the Siteman Cancer Center.

The following steps must be taken before registering patients to this study:

1. Confirmation of patient eligibility by Washington University
2. Registration of patient in the Siteman Cancer Center OnCore database
3. Assignment of unique patient number (UPN)

Once the patient has been entered in the Siteman Cancer Center OnCore database, the WUSM coordinator will forward verification of enrollment and the UPN via email.

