4.1 Confirmation of Patient Eligibility

Confirm patient eligibility by collecting the information listed below and scanning and emailing it to the research coordinator listed in the *Siteman Cancer Center Clinical Trials Core Protocol Procedures for Secondary Sites* packet at least one business day prior to registering patient:

1. Your name and contact information (telephone number, fax number, and email address)
2. Your site PI's name, the registering MD's name, and your institution name
3. Patient's race, sex, and DOB
4. Three letters (or two letters and a dash) for the patient's initials
5. Currently approved protocol version date
6. Copy of signed consent form (patient name may be blacked out)
7. Planned date of enrollment
8. Completed eligibility checklist, signed and dated by a member of the study team
9. Copy of appropriate source documentation confirming patient eligibility

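### Inclusion 8 asks for fewer contraceptive methods than section 5.4 and for nothing after treatment; the 7-day pregnancy test is also counted from an undefined date

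*Combined protocol and SAP*

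**What the plan says.** The rules for women of childbearing potential are spread over several parts of the protocol.

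- **Section 5.4** says these women are "required to use two forms of acceptable contraception, including one barrier method, during participation in the study and for 90 days" after the last palbociclib dose. It requires a "negative pregnancy test within 7 days prior to the first dose of palbociclib". If a patient "becomes pregnant during therapy or within 90 days after the last dose of palbociclib, the investigator must be notified".
- **Section 3.1, inclusion 8** asks the woman to agree to "adequate contraception (hormonal or barrier method of birth control, abstinence) prior to study entry and for the duration of study participation".
- **Section 3.2, exclusion 10** requires a "negative pregnancy test within 7 days of study entry". The protocol does not define study entry.
- **Section 8.1.9** asks for effective contraception during the trial and for at least 90 days after treatment. It gives no number of methods and leaves the judgment to the principal investigator or a delegate. It wants a negative test before treatment but sets no day limit.
- **Section 10.0 (calendar)** ticks β-hCG at screening only, and screening may take place up to 2 weeks before therapy starts. Footnote 1 says who is tested, not when.

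On sequence, section 4.0 states: "Patients must not start any protocol intervention prior to registration through the Siteman Cancer Center". Section 4.1 asks for a "Completed eligibility checklist, signed and dated by a member of the study team" before registration.

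**The concern.** Staff are most likely to screen from the eligibility criteria and the calendar, and those are the places with the looser wording. A woman on one hormonal method passes inclusion 8, yet does not meet 5.4 from her first day on treatment. What she agrees to under inclusion 8 also has no stated end beyond participation, while 5.4 and 8.1.9 both look 90 days past treatment.

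The stake is patient safety. Section 8.1.9 says that fertility and teratology studies of palbociclib have not been carried out, so the contraception rule is a main protection against fetal exposure. Nothing here touches the neutropenia endpoint, the 47-patient sample size or the decision rule.

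**Working it through.** The plan has no calculated figure to reproduce. The check sets the rules side by side and then bounds the age of the pregnancy test.

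**Step 1. Contraception**

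| Source | Methods | Before study entry | After treatment |
|---|---|---|---|
| Inclusion 8 | 1 (hormonal or barrier), or abstinence | yes | none stated |
| Section 5.4 | 2, one a barrier | not mentioned | 90 days after last palbociclib dose |
| Section 8.1.9 | number not given | not mentioned | at least 90 days |

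A woman using one hormonal method satisfies inclusion 8 and is one method short of 5.4. If participation is read generously to include the 30-day follow-up in sections 5.6 and 7.7, inclusion 8 still stops about 90 − 30 = 60 days before 5.4 does. In one respect inclusion 8 asks for more: it covers the time before study entry, and 5.4 does not.

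**Step 2. Pregnancy test**

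Let g be the number of days from registration to first dose. The documents give no value and no maximum. Section 4.0 implies g ≥ 0.

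- *Reading A, study entry is the first dose.* The oldest test allowed by exclusion 10 is 7 days. Excess over 5.4: 7 − 7 = 0 days.
- *Reading B, study entry is registration (assumption).* The oldest test allowed by exclusion 10 together with the 2-week calendar window is min(7 + g, 14) days. Excess over 5.4: min(g, 7) days.

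| g (days, assumed) | Oldest test, Reading B | Excess over 5.4 |
|---|---|---|
| 0 | 7 | 0 |
| 1 | 8 | 1 |
| 3 | 10 | 3 |
| 7 or more | 14 | 7 |

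The range over both readings is 0 to 7 days. The 14-day cap is the calendar's 2 weeks; I have not added the ±3-day visit window to it.

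**Step 3. Does following 5.4 satisfy every other rule?**

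Not entirely. The duty before study entry in inclusion 8 is outside 5.4. Under Reading B, suppose registration is 10 days before the first dose and the test 1 day before it. The test meets 5.4 but falls 10 − 1 = 9 days after registration, outside a 7-day limit counted from registration.

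**The case against.** The strongest reply is that 5.4 is mandatory and stands alongside the eligibility criteria, so a compliant site must apply it whatever inclusion 8 says. Eligibility is also confirmed centrally by Washington University before registration, from a signed checklist and source documents. That checklist is not in the documents and may already apply 5.4. All this stands and lowers the practical risk. It does not repair the text: I found no cross-reference or precedence clause telling a site that inclusion 8 is incomplete.

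On the test, exclusion 10 already contains a 7-day limit. In the same list, exclusion 6 names registration explicitly while exclusion 10 says study entry, which suggests that the authors meant something else by it. That favours Reading A, with no excess. A reader might infer that the protocol lets a 14-day-old test through. The documents do not support that as a general statement: it needs exclusion 10 to be ignored, or study entry to mean registration with a gap of at least 7 days, and even then 5.4 forbids it.

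A third reply is that for these women "concurrent ovarian suppression for pre- or peri-menopausal women is required". This reduces the risk of pregnancy, but the protocol imposes contraception and testing as well, so it does not treat suppression as a substitute.

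**Conclusion.** The contraception mismatch is real and needs no assumption: one method or abstinence against two including a barrier, and no stated post-treatment period against 90 days. The test mismatch is secondary, at 0 to 7 days, and anything above 0 rests on reading study entry as registration. It applies only to women of childbearing potential, whose number the documents do not give.

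Two stronger readings should be resisted. A reader might infer that the 90-day protection is missing; it is not, since 5.4 and 8.1.9 both state it and 5.4 extends pregnancy notification to the same point. A reader might also infer that 5.4 is the strictest rule in every respect and can simply replace the others; it cannot, because it omits the period before study entry.

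This is a minor correction, worth making because it concerns a safety rule.

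**What to change.** 1. Amend inclusion 8 to two forms including one barrier method, keeping the existing duty before study entry, through participation and for 90 days after the last palbociclib dose.
2. Re-anchor exclusion 10 to the 5.4 wording, a "negative pregnancy test within 7 days prior to the first dose of palbociclib", and put the same limit in calendar footnote 1.
3. In 8.1.9, cross-refer to 5.4 for the contraception rule and the test window only.

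Two matters should be left for the investigator to decide and state. One is whether abstinence is acceptable. The other is who counts as of childbearing potential: 5.4 includes women with a tubal ligation or amenorrhea, while 8.1.9 exempts those who are surgically sterile or postmenopausal. Sending 8.1.9 to 5.4 for the definition would settle that second question without discussion.

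The cost is a text-only protocol amendment, with the checklist aligned if it does not already apply 5.4. Sample size, endpoints and analysis are unchanged.
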